Title: Comparison of 3 versus 6-Month Use of Professional Continuous Glucose Monitoring in the Treatment of Poorly Controlled, Non-Insulin Using T2DM Patients in a Primary Care Setting

NCT#: NCT03067480

Date: December 4th 2018

Research Abstract Proposal

Comparison of 3 versus 6-Month Use of Professional Continuous Glucose Monitoring in the Treatment of Poorly Controlled, Non-Insulin Using T2DM Patients in a Primary Care Setting

Primary Objective:

1. To determine whether 3-month versus 6-month professional CGM utilization improves time spent in target range of 70-140mg/dl in patients with poorly controlled T2DM not treated with insulin.

Secondary Objectives:

1. To determine whether 3-month versus 6-month professional CGM utilization improves hemoglobin A1c in patients with T2DM not treated with insulin.
2. To determine whether 3-month versus 6-month professional CGM utilization leads to more treatment intensification.

Background

For prescribers, the hemoglobin A1c (HbA1c) lab value is the most common monitoring used in primary care to assess diabetes control and determine if pharmacotherapy modification is warranted. For patients with type 2 diabetes (T2DM), self-monitoring blood glucose (SMBG) results may be performed to evaluate diabetes control, but these results must be communicated to the clinician in an effective and timely manner for the data to be useful in creating a patient-centered plan.¹ Structured SMBG plans that include a 7-point glucose profile over 3 days (fasting, pre and 2-hour post-meal, and bedtime) has demonstrated improved glycemic control in poorly controlled T2DM patients (HbA1c \geq 7.5%) not treated with insulin.² In this study, prescribers were more likely to make treatment changes when structured SMBG occurred compare to no structured SMBG. However, structured SMBG protocols are rarely implemented in primary care offices. Overall, the usefulness and cost-effectiveness of SMBG in T2DM patients treated with non-insulin therapies is conflicting and the American Diabetes Association (ADA) has assigned it an evidence-based grade of “E” for expert opinion.^{1,3} Professional continuous glucose monitoring (CGM) could represent another opportunity for prescribers to assess glycemic control over a 3-day period.

Professional CGM measures interstitial glucose every 5 minutes via a glucose-oxidase-impregnated membrane during a 3–5 day period.⁴ The patient wearing professional CGM is blinded to the repeated measurements and the data is stored for retrospective analysis. The durable equipment used to perform professional CGM is owned and maintained by the practice site or clinician and can be used regularly with a variety of patients. Currently, insurance companies often determine the use of professional CGM in T2DM and frequency of use is variable. There is no data available comparing glycemic control in non-insulin treated patients with T2DM when professional

CGM is utilized at different frequencies or examining the best use of professional CGM in this subset of patients. This population represents a significantly large number of patients who are typically treated in primary care settings without an endocrinologist. The results of this trial could assist Medtronic in marketing professional CGM products to primary care providers.

Given the usefulness of the glycemic data provided by professional CGM, I hypothesize that patients who wear the professional CGM at 3-month intervals when spend more time in target range than those wear it at 6-month intervals. This hypothesis will be addressed in the following specific aims:

Specific Aims:

1. To determine the percent time spent in target range of 70-140mg/dl in poorly controlled patients with T2DM not treated with insulin.

Patients not receiving any insulin treatment with an HbA1c $\geq 7.5\%$ before their scheduled primary care appointment will be invited to participate in the study and wear professional CGM for at least 3 days at either 3 intervals (baseline, 3-month and 6-month) or 2 intervals (baseline and 6-month). After removal, the downloaded report will provide quantitative data to determine the percent of time spent in the target range. The 6-month data will be analyzed to determine if frequency of professional CGM wear positively affects time spent in target range.

2. To determine the hemoglobin A1c levels in poorly controlled patients with T2DM not treated with insulin.

Patients who consent to the study will have their HbA1c levels measured in our central lab at the clinic and recorded in the electronic medical record (EMR). This data is easily retrievable for reporting and would be analyzed to determine if frequency of professional CGM wear would positively affect HbA1c levels.

3. To determine treatment modification in poorly controlled patients with T2DM not treated with insulin.

The EMR documents current and previous medication therapies including newly prescribed medications, increased or decreased dosage changes or termination of prescribed medication. Only FDA-approved medications for the treatment of type 2 diabetes will be monitored. The type of treatment modification and their frequencies can be retrieved from the EMR and analyzed to determine if frequency of professional CGM wear affects these outcomes.

Sample Size and Rationale

A calculated sample size of 20 patients will be needed to detect a 15% effect size (e.g., mean of 60% vs. 75% of time in target range) with a standard deviation of 10 and 90% power. Assuming a 25% drop out, planned enrollment is 25 patients with poorly

controlled T2DM (defined as last two consecutive HbA1c values between 7.5 – 10%) and who have not received insulin within the last 3 months.

Study Design

6-month, Prospective, Randomized, Single Center

Inclusion Criteria

- 18 years or older with a diagnosis of T2DM with a scheduled office visit with primary care provider within the next 4 weeks
- Last 2 HbA1c values between 7.5 – 10% measured in the last 12 months
- Treated with non-insulin therapies or therapeutic lifestyle changes
- Never worn professional CGM or have not worn in last 12 months
- Willing to perform requirements needed for professional CGM

Exclusion Criteria

- Current or previous treatment with any insulin within 3 months at baseline

Protocol or Study Plan

1. Identify patients via electronic medical record reporting based on inclusion criteria.
2. Contact and screen prospective participants either via phone call explaining the research project and objectives.
3. In patient expresses interest, complete the consent process and randomize participant into either 3-month or 6-month professional CGM.
4. **Baseline Visit**
 - a. Assign de-identified code to participate for confidentiality protection.
 - b. Measure demographic information, baseline HbA1c levels, baseline medication therapies and doses.
 - c. Place professional CGM placement and provide patient education for successful 3-day wear.
 - d. Schedule follow-up professional CGM placement visits at either
 - i. 3-month and 6-month or
 - ii. 6-month only.
 - e. Confirm scheduled primary care physician follow-up appointment(s).
 - f. After patient returns CGM, download 3 color copies of CGM reports (one for physician, patient and research records)
 - g. Provide downloaded professional CGM reports to primary care physician prior to patient appointment for review. Inform physician a Certified Diabetes Educator (CDE) is available for consultation, as needed.
 - i. Contingency Plan – if in the event any reading are < 40mg/dl or > 400mg/dl, the physician will be contacted that same day through

the EMR system instead of waiting till the next scheduled appointment

5. 3-Month Visit

- a. if randomized to 3-month CGM arm
 - i. Confirm patient CGM placement visit approximately 1 week in advance.
 - ii. Place professional CGM placement and provide patient education for successful 3-day wear.
 - iii. Record any new HbA1c results and changes to medication therapies and/or doses.
 - iv. Confirm 6-month professional CGM placement visits.
 - v. Confirm scheduled primary care physician follow-up appointment(s).
 - vi. After patient returns CGM, download 3 color copies of CGM reports (one for physician, patient and research records)
 - vii. Provide downloaded professional CGM reports to primary care physician prior to patient appointment for review. Inform physician a Certified Diabetes Educator (CDE) is available for consultation, as needed.
 1. Contingency Plan – if in the event any reading are < 40mg/dl or > 400mg/dl, the physician will be contacted that same day through the EMR system instead of waiting till the next scheduled appointment
- b. If patient is NOT scheduled to receive CGM, then at 3 months:
 - i. Contact patient by telephone and ask to perform SMBG four times daily (before all meals and bedtime) for 3 days and bring the results to their scheduled physician visit

6. 6-Month Visit

- a. Confirm patient CGM placement visit approximately 1 week in advance.
- b. Place professional CGM placement and provide patient education for successful 3-day wear.
- c. Record any new HbA1c results and changes to medication therapies and/or doses.
- d. Confirm scheduled primary care physician follow-up appointment(s).
- e. After patient returns CGM, download 3 color copies of CGM reports (one for physician, patient and research records)
- f. Provide patient with \$50 gift card.
- g. Provide downloaded professional CGM reports to primary care physician prior to patient appointment for review. Inform physician a Certified Diabetes Educator (CDE) is available for consultation, as needed.
 - i. Contingency Plan – if in the event any reading are < 40mg/dl or > 400mg/dl, the physician will be contacted that same day through the EMR system instead of waiting till the next scheduled appointment

7. Analyze and report data.

Schedule with key milestones

Fall 2016 – begin recruitment

Spring 2017 – all participants completed 3-month visit

Fall 2017 – all participants completed 6-month visit

Biostatistics and Data Analysis

Descriptive statistics including mean, standards deviation, frequency, etc. will provide the summary information for this study. A linear regression will be used to investigate if frequency of professional CGM wear (independent variable) positively affects time spent and HbA1C level (outcome variables) in target range. An appropriate transformation will be used if the normality is severely violated. Meanwhile, the significant changes of HbA1C overtime will be used to determine with a longitudinal data analysis. More specifically, repeated measure approach will be used for 3 intervals (baseline, 3-month and 6 month) and matched pair t-test will be used for 2 intervals (baseline and 6-month). Frequencies of in treatment modification would be analyzed using Chi-Square test. A $p < 0.05$ will be used to indicate statistically significant. All data analyses will be performed with SAS (version 9.4 Cary, NC, USA).

Start Date and End Date

October 1st 2016 – October 1st 2017 (approximate)

References

3. American Diabetes Association. Glycemic targets. Sec. 5. In Standards of Medical Care in Diabetes 2016. *Diabetes Care* 2016;39(Suppl. 1):S39–S46.
4. Blevins TC. Professional Continuous Glucose Monitoring in Clinical Practice 2010. *Journal of Diabetes Science and Technology.* 2010;4(2):440-456.

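### Time in range is compared on the month-6 CGM wear alone, with no provision for the 25% expected to drop out, so by default the primary result covers completers only and carries a bias of unknown direction

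*Combined protocol and SAP*

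**What the plan says.** Aim 1 in Specific Aims fixes the scoring time of the primary endpoint: "The 6-month data will be analyzed to determine if frequency of professional CGM wear positively affects time spent in target range". One arm wears CGM at baseline, month 3 and month 6; the other at baseline and month 6 only. At month 3 the second arm has no CGM. Protocol or Study Plan, item 5b, gives the instruction instead: "Contact patient by telephone and ask to perform SMBG four times daily (before all meals and bedtime) for 3 days". Month 6 is therefore the only post-baseline wear that both arms share.

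Biostatistics and Data Analysis names the model: "A linear regression will be used to investigate if frequency of professional CGM wear (independent variable) positively affects time spent". The longitudinal method in the same paragraph is for another endpoint: "the significant changes of HbA1C overtime will be used to determine with a longitudinal data analysis".

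Sample Size and Rationale deals with attrition in one clause: "Assuming a 25% drop out, planned enrollment is 25 patients". The documents name no analysis set, no missing-data method and no sensitivity analysis for time in range.

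**The concern.** Ordinary linear regression uses only patients whose outcome is observed. A patient who leaves before the month-6 wear has no outcome and is removed without any decision being recorded. The comparison is then between the completers of each arm, not between the groups that were randomised.

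That matters if leaving is related to glycaemic control differently in the two arms. Patients know which schedule they follow; the blinding described in Background covers the glucose readings during a wear, not the arm. At month 3 one arm has a further sensor placement, a device return and its own copy of a report, while the other has a telephone request for self-monitoring. Both the reasons for leaving and the number who leave could therefore differ by arm. With 9 or 10 completers per arm, a few unscored patients can move the estimate by a noticeable fraction of its standard error, and nothing in the planned report would show it.

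**Working it through.** **Inputs from the plan (Sample Size and Rationale; Biostatistics and Data Analysis):** difference 15 points, SD 10, power 90%, significance level 0.05, 20 evaluable, 25 enrolled, 25% drop out.

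**Assumptions, not in the plan:** allocation 13 (3-month arm) and 12 (6-month arm); 6 patients lost; unadjusted two-sided comparison; D = the number of points by which an arm's drop-outs would have scored below that arm's completers.

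**1. The plan's figure.** n per arm = 2 × (1.960 + 1.282)² × 10² / 15² = 9.3, rounded up to 10, so 20 in total. This reproduces with a two-sided test. A one-sided test gives 8 per arm (16) and does not.

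**2. How many are unscored.** 0.25 × 25 = 6.25, about 6. That leaves 25 × 0.75 = 18.75, about 19, with a month-6 value. (25 is 20 × 1.25, whereas 20 / 0.75 gives 27. That is a separate power point and is not needed here.)

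**3. Precision among completers.** With 10 and 9 completers, SE = 10 × √(1/10 + 1/9) = 4.59. With 17 df, t = 2.11, so the smallest significant difference is 2.11 × 4.59 = 9.7 points. For 11 and 8 completers the figures are 4.65 and 9.8.

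**4. Bias of the completer difference (3-month minus 6-month arm):**

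bias = (lost in 3-month arm / 13) × D₃ − (lost in 6-month arm / 12) × D₆

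Each cell gives the bias in points. In brackets is the two-sided rejection rate when there is no true difference among all randomised patients, from the noncentral t distribution with noncentrality bias / SE.

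| Lost, 3-month and 6-month arm | Shift applies to | D = 5 | D = 10 | D = 15 |
|---|---|---|---|---|
| 3 and 3 | 3-month arm only | +1.2 (6%) | +2.3 (8%) | +3.5 (11%) |
| 3 and 3 | 6-month arm only | −1.25 (6%) | −2.5 (8%) | −3.75 (12%) |
| 3 and 3 | both arms equally | −0.1 (5%) | −0.2 (5%) | −0.3 (5%) |
| 4 and 2 | 3-month arm only | +1.5 (6%) | +3.1 (10%) | +4.6 (16%) |
| 2 and 4 | 6-month arm only | −1.7 (6%) | −3.3 (10%) | −5.0 (17%) |
| 4 and 2 | both arms equally | +0.7 (5%) | +1.4 (6%) | +2.1 (7%) |

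Examples: 3/13 × 15 = 3.5; 3/12 × 15 = 3.75; 4/13 × 15 = 4.6; 4/12 × 15 = 5.0. The small remainder in the third row arises only because 3/13 and 3/12 differ.

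**5. Tipping points, shift in the 3-month arm only, SE held fixed.**
- Observed difference of 12 points (chosen for illustration): (12 − 9.7) / (3/13) = about 10, or / (4/13) = about 7.5.
- The plan's 15 points: (15 − 9.7) / (3/13) = about 23, or / (4/13) = about 17.

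**The case against.** The strongest reply is that the documents do not show which arm would lose more patients, or which kind. A reader might infer that completer analysis here favours the 3-month arm, for instance because a patient who will not wear the sensor again, or who is discouraged by a report, would leave that arm alone. The protocol does not support this. Both arms wear CGM at baseline and must wear it again at month 6, and both receive a patient copy of the baseline report (Protocol or Study Plan, items 4 and 6). Only the month-3 report is confined to one arm, and the other arm has its own month-3 burden of self-monitoring four times a day. This part of the objection stands, and the working therefore shows both directions.

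It is also fair that the larger shifts are not modest. D = 10 is a full planned SD and D = 15 equals the whole planned effect. At D = 5 the error rate barely moves, and a difference of 15 points would survive every shift up to 15. A reader might infer that a small departure would usually overturn the result; that holds only for a difference not far above the 9.7-point threshold.

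Finally, the plan never says that it will analyse completers. The restriction follows by default from the named model. The 25% is a planning assumption, and there are retention measures at month 6 (a confirmation about a week ahead and a gift card). These points limit the expected size of the problem. They do not supply the missing analysis set, missing-data method or sensitivity analysis.

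**Conclusion.** The concern holds as an omission with a bias of uncertain sign. As written, the primary comparison rests by default on about 19 of 25 patients, and the larger enrolment does nothing about who is missing. Bias is essentially zero if drop-outs differ from completers by the same amount and in the same proportion in both arms. If the shift is confined to one arm, it is about 1.2 to 3.5 points toward the 3-month arm or 1.25 to 3.75 points against it with 3 and 3 lost, and reaches 4.6 to 5 points at D = 15 with a 4 and 2 split. Two-sided error then runs from about 6% at D = 5 to about 16-17% at D = 15 in the uneven splits. These figures rest on the plan's SD and drop-out rate and on assumed values of D, of the split by arm and of near-equal allocation. The documents do not support a claim that the plan is tilted toward finding a benefit. They do support saying that its report could not tell a reader whether the result depends on the missing patients. The change is worth making because it is cheap and alters what the trial can conclude.

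**What to change.** In Biostatistics and Data Analysis, after the linear-regression sentence, add:

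> All randomised patients are analysed in their assigned arm. The regression on patients with a month-6 wear is reported adjusted for baseline time in range. As a sensitivity analysis, missing month-6 time in range is multiply imputed from arm, baseline time in range, baseline HbA1c and, where available and permitted by consent, month-6 HbA1c from the EMR. Imputed values are then shifted up and down in steps of 5 points, in each arm separately and in both together, and the shifts at which p crosses 0.05 are reported with drop-out numbers by arm. If small shifts change the conclusion, it is stated as dependent on completers.

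The month-3 CGM should not be carried forward, because it exists in one arm only. No fixed shift, such as 10 points, should be set as the test of robustness, since nothing in the documents would justify one.

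Cost: a few sentences and a short SAS program, with no added patients, visits or procedures. Imputation with about 25 patients is imprecise. With only the outcome missing, imputing from baseline values adds little to a baseline-adjusted regression unless a month-6 HbA1c exists, so the tipping-point step carries most of the information. The conclusion may have to be worded less favourably.

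### Enrolling 25 with the stated 25% dropout leaves about 19 completers, not the 20 the plan says it needs; 25 covers only 20% dropout

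*Combined protocol and SAP*

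**What the plan says.** The Sample Size and Rationale section gives the target as "A calculated sample size of 20 patients will be needed to detect a 15% effect size", illustrated as "e.g., mean of 60% vs. 75% of time in target range", "with a standard deviation of 10 and 90% power". The next sentence sets recruitment: "Assuming a 25% drop out, planned enrollment is 25 patients". No other enrolment figure, definition of dropout or rule for replacing patients who leave appears in the document.

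The sample-size text names no sizing method, alpha, sidedness or allocation ratio. Study Design says only "6-month, Prospective, Randomized, Single Center". Biostatistics and Data Analysis supplies a 0.05 significance threshold without saying one- or two-sided, and the primary analysis: "A linear regression will be used to investigate if frequency of professional CGM wear (independent variable) positively affects time spent".

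**The concern.** A dropout rate is a fraction of those enrolled. Applied to 25 patients, a 25% rate leaves fewer than the 20 the plan says are necessary. A reader is told that enrolment absorbs a 25% loss when it absorbs 20%.

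Losses fall directly on the primary comparison. Specific Aim 1 rests on the 6-month CGM data, so a patient who leaves before that wear has no primary value, and the analysis section describes no handling of missing data. At stake are one or two completers and a little power in a very small trial. Anyone later judging the attrition or a null result would start from the wrong allowance.

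**Working it through.** **Inputs.** From Sample Size and Rationale: 20 needed, difference 15 percentage points (60% against 75%), SD 10, power 90%, dropout 25%, enrolment 25. From Biostatistics and Data Analysis: alpha 0.05. Assumed because not stated: two-sided test, 1:1 allocation.

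**Step 1: reproduce the 20.** Normal approximation, patients per arm = 2 × (z for alpha + z for power)² × (SD/difference)².

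- Two-sided: 2 × (1.960 + 1.282)² × (10/15)² = 9.34, so 10 per arm and 20 in total. This matches the plan.
- One-sided: 7.61, so 8 per arm and 16 in total. By one-sided t-test the smallest total is 17 (9/8, power 90.3%). Neither matches.
- Two-sided t-test: 10 per arm gives 88.7%; reaching 90% takes 11 per arm (22 in total, 91.7%).

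The stated 20 is therefore consistent with a two-sided normal approximation.

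**Step 2: the dropout allowance.**

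- Expected completers: 25 × (1 − 0.25) = 18.75.
- Dropout at which 25 retains 20: 1 − 20/25 = 20%.
- Enrolment that retains 20 at 25% dropout: 20/(1 − 0.25) = 26.67, so 27 (27 × 0.75 = 20.25; 26 × 0.75 = 19.5 falls short).
- The plan's figure equals 20 × 1.25 = 25, which is consistent with adding 25% to the target rather than dividing by 0.75. The document shows no working, so this is an inference.
- If each patient independently has a 25% chance of dropping out, the probability that at least 20 of 25 complete is 0.378. With 27 enrolled it is 0.643.

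**Step 3: effect on power** (15 points, SD 10, alpha 0.05, arms as equal as possible).

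| Completers (arms) | Two-sided t | Two-sided normal | One-sided t |
|---|---|---|---|
| 20 (10/10) | 88.7% | 91.8% | 94.3% |
| 19 (10/9) | 86.8% | 90.4% | 93.1% |
| 18 (9/9) | 84.8% | 88.9% | 91.9% |

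The two-sided t-test is equivalent to the planned regression with a single arm term. On that basis, going from 20 to 19 completers costs 88.7 − 86.8 = 1.9 points, and going to 18 costs 88.7 − 84.8 = 3.9. On the normal approximation the costs are 1.4 and 2.9 points. The separate gap between the claimed 90% and 88.7% at 20 completers (1.3 points) comes from the sizing method, not from dropout.

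**Step 4: sensitivity.** If losses leave unequal arms at 19 completers, two-sided t power is 86.0% at 11/8 and 84.4% at 12/7. Averaged over random 25% loss from a 13/12 start, it is 85.1%. The difference detectable with 90% power (two-sided t) is 15.3 points at 20 completers, 15.8 at 19 and 16.3 at 18.

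**The case against.** The best defence is that 25 does support the power claim under the one method that reproduces 20. The unrounded two-sided normal requirement is 2 × 9.34 = 18.68 patients. Dividing correctly, 18.68/0.75 = 24.9, which rounds up to 25, and 18.75 expected completers exceed 18.68. On that reading the trial is not under-enrolled and multiplication may never have been used. It also follows that quoting t-test power in the correction brings in a second issue, that two-sidedness and 1:1 allocation are assumptions, and that the document is dated December 2018, after the planned end of about October 2017, so the correction is editorial.

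Much of this stands. Power does stay at about 90% under the normal approximation, the mechanism is not provable, and the cost in power is small. But the plan says it needs 20, not 18.68, and the defence does not make 20, 25% and 25 agree. The t-based figures are the relevant ones for the planned regression on arm, provided their assumptions are stated and the 1.3 points due to sizing method are kept apart from the dropout effect.

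**Conclusion.** The concern holds as a minor arithmetic inconsistency. The head count is certain and needs no assumption about test, sidedness or allocation: 25 enrolled at 25% dropout gives 18.75 completers against a stated 20, and the real allowance is 20%.

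The power consequence is held with moderate confidence because it rests on a two-sided 0.05 test and 1:1 allocation. It is about 2 to 4 points by t-test for 19 or 18 completers, with power roughly at the planned 90% by normal approximation. It is not a material loss of power, and no endpoint, test or type I error rate changes.

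**What to change.** Restate the enrolment sentence in one of two ways, without recruiting more patients:

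1. *25 enrolled with 25% dropout gives about 19 evaluable patients and about 85–87% power (two-sided t-test, alpha 0.05, 1:1 allocation) for a 15-percentage-point difference with SD 10.*
2. *25 enrolled retains 20 completers at 20% dropout (88.7% power by two-sided t-test, alpha 0.05, 1:1 allocation).*

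The first keeps the plan's dropout assumption. The second changes it to 20%, for which the document gives no support, so the sponsor would need to justify that rate. With either, the sponsor should confirm the sidedness and allocation, which the plan now omits. If the normal approximation is kept as the sizing method, the text should say so and give its figures (90.4% at 19, 91.8% at 20).

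The cost is one sentence, with no extra patients and no change to the analysis. Either the stated power or the stated dropout allowance becomes slightly less favourable.

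### The primary between-arm regression does not name baseline time in range as a covariate, although both arms are to have it measured and only about 18 to 20 patients are expected to complete.

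*Combined protocol and SAP*

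**What the plan says.** The between-arm analysis is described in one sentence of Biostatistics and Data Analysis: "A linear regression will be used to investigate if frequency of professional CGM wear (independent variable) positively affects time spent and HbA1C level". No other predictor is listed. Under Specific Aims, Aim 1 fixes the time point: "The 6-month data will be analyzed to determine if frequency of professional CGM wear positively affects time spent in target range".

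Baseline monitoring is planned for everyone. Aim 1 has patients "wear professional CGM for at least 3 days at either 3 intervals (baseline, 3-month and 6-month) or 2 intervals (baseline and 6-month"), and the Baseline Visit steps include "Place professional CGM placement and provide patient education for successful 3-day wear". A copy of each downloaded report goes to the research records, and Aim 1 says percent time in range is obtained from that report.

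For HbA1c, the baseline value appears only in the analyses of change over time: repeated measures for three time points, and "matched pair t-test will be used for 2 intervals (baseline and 6-month"). Neither is written for time in range, and neither is described as a comparison of the arms.

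On size, Sample Size and Rationale asks for 20 patients (15-point difference, SD 10, 90% power) and continues: "Assuming a 25% drop out, planned enrollment is 25 patients".

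**The concern.** A baseline measurement of the primary outcome is usually the strongest single predictor of its later value. The plan arranges to collect it in both arms and then gives it no part in the primary comparison. In a large trial this would matter little. Here the comparison rests on about nine or ten patients per arm, and expected completers fall below the 20 on which the power claim depends.

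Two things are at stake. The confidence interval may be wider than it need be. And because the plan neither names covariates nor rules them out, the choice between an adjusted and an unadjusted result stays open until the data are seen. With so few patients the two could differ noticeably.

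**Working it through.** **Inputs.** From Sample Size and Rationale: difference 15 points, SD 10, power 90%, N = 20, 25 enrolled, 25% drop-out. From Biostatistics and Data Analysis: significance level 0.05. Assumed because not stated: two-sided test, 1:1 allocation, and the correlation ρ between baseline and 6-month time in range, shown over a range.

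**1. The plan's own figure.** The normal-approximation formula gives n per arm = 2(1.960 + 1.282)² × 10² / 15² = 9.34, rounded up to 10, so 20 in total. This matches the plan, with no baseline adjustment in it. A one-sided test would give 16, which does not match.

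**2. Expected completers.** 25 × 0.75 = 18.75, so 18 or 19; 20 if the target is met.

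**3. Unadjusted power.** SE = 10√(1/n₁ + 1/n₂), noncentral t on N − 2 df. At 9+9, SE = 4.71 and power is 84.8%. At 10+9 it is 86.8%. At 10+10, SE = 4.47 and power is 88.7%, because the t-test gives slightly less than the normal approximation.

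**4. Adjusted analysis.** SE = 10√(1 − ρ²) × √(1/n₁ + 1/n₂ + D²/SSw), on N − 3 df. D is the chance difference in baseline means and SSw the within-arm baseline sum of squares. Averaged over randomisations, the D term multiplies the variance by 1 + 1/(N − 4): 1.071 at N = 18 and 1.063 at N = 20. Worked case at 9+9 with ρ = 0.5: variance factor 0.75 × 1.071 = 0.804; SE = 4.71 × √0.804 = 4.23; half-width = 2.131 × 4.23 = 9.0 points.

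**5. Results.** These are averaged over simulated normal baselines.

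| Completers | Quantity | Unadjusted | ρ = 0 | 0.25 | 0.3 | 0.5 | 0.7 |
|---|---|---|---|---|---|---|---|
| 9+9 | Power, % | 84.8 | 82.0 | 84.3 | 85.3 | 91.2 | 97.9 |
| 9+9 | 95% CI half-width, points | 10.0 | 10.4 | 10.1 | 9.9 | 9.0 | 7.4 |
| 10+10 | Power, % | 88.7 | 86.6 | 88.6 | 89.5 | 94.2 | 98.9 |
| 10+10 | 95% CI half-width, points | 9.4 | 9.7 | 9.4 | 9.3 | 8.4 | 6.9 |

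Full simulation of 200,000 trials at 9+9 gave 81.9/84.3/85.3/91.1/97.8% for the five correlations, in agreement with the table.

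**6. Thresholds.** Adjusted and unadjusted power are equal at ρ of about 0.27 (9+9) or 0.26 (10+9 and 10+10). Adjusted power reaches 90% at ρ of about 0.47 (9+9), 0.41 (10+9) or 0.33 (10+10).

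**7. Chance imbalance.** If the baseline SD is also 10 (an assumption), the baseline difference has SE 4.71 with 9 per arm and 4.47 with 10. A gap above 5 points then has probability 29% or 26%. A 5-point gap moves the unadjusted 6-month difference by ρ × 5: 1.5, 2.5 or 3.5 points at ρ = 0.3, 0.5 or 0.7. This is the same gain as in step 5, seen in a single trial; it is not additional.

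**The case against.** The strongest reply is that this is a preference for efficiency, not an error. Randomisation makes the unadjusted comparison valid, and the plan does not forbid covariates. That is true, and it is why the point is a recommendation and not a condition of validity.

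Second, the gain depends on a correlation the documents do not give, and features of the design could weaken it. Eligibility restricts HbA1c to 7.5–10%, each wear may be as short as three days, and physicians receive the baseline report and may change treatment. At ρ = 0.3 the gain at 9+9 is half a percentage point. This stands, so the benefit can be called only probable. The break-even near 0.27 is nonetheless low for the same measure repeated in the same patient.

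Third, a completer without a usable baseline recording would drop out of the adjusted model. If one of 18 is lost (9+8), adjusted power is 82.7/85.5/89.0% at ρ = 0.3/0.4/0.5, against 84.8% for the unadjusted 9+9, and break-even rises to just under 0.4. If two are lost (8+8), the figures are 79.9/82.9/86.8% and break-even is about 0.45. This stands, and the fix needs a rule for it. Randomisation also precedes the baseline wear in the study plan. However, the arms' monitoring schedules diverge only at 3 months, so the baseline recording remains a legitimate covariate.

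Fourth, part of the power shortfall belongs to the sample-size section: dividing by the retention rate gives 20/0.75 = 26.7, or 27 enrolled, where the plan has 20 × 1.25 = 25. That is a separate matter, and adjustment does not replace correcting it. Lastly, the figures concern time in range only. The documents give no SD or target difference for HbA1c, so the gain there cannot be sized.

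**Conclusion.** The point holds. The plan names one predictor for the between-arm regression and leaves baseline time in range unused, though both arms are to supply it. The analysis as written is valid but probably less precise than it could be.

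At 9+9 completers, adjustment changes power by about −3 points at ρ = 0 (82.0 − 84.8), +6 at 0.5 (91.2 − 84.8) and +13 at 0.7 (97.9 − 84.8). The interval half-width goes from 10.0 to 10.4, 9.0 and 7.4 points respectively. These figures rest on the plan's SD and difference, a two-sided 0.05 test, equal arms, normal data, a usable baseline recording for every completer, and an assumed ρ. The omission itself is certain from the text; the size of the gain is not.

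**What to change.** State the primary model as 6-month percent time in 70–140 mg/dl regressed on randomised arm and baseline percent time in range. Report the adjusted difference with its 95% CI. Use the same form for 6-month HbA1c with baseline HbA1c as covariate, and keep the over-time tests within each group as descriptive.

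Three clarifications belong with it:

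- Name the predictor as randomised arm. The 3-Month Visit section already speaks in those terms ("if randomized to 3-month CGM arm").
- Define the baseline value as time in range from the baseline wear.
- Say what happens to a completer whose baseline wear fails, so that the patient stays in the analysis; for example, replace the missing covariate with the mean of all observed baseline values, pooled over arms.

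The cost is a line or two of text and one degree of freedom, with up to about 3 points of power at 9+9 if the correlation is near zero. No new data are needed. The change must be fixed before the 6-month data are examined. The document is dated December 2018 and its schedule ends in fall 2017, so that may no longer be possible. If the data have been examined, report the adjusted result as a labelled sensitivity analysis beside the unadjusted one.
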